7.5.8 Additional Testing Requirements During Neurapheresis

At 36 hours (± 4 hr) and 72 hours (± 4 hr) or end of catheter in-dwelling (whichever comes first), a venous blood sample and CT are required. Timing should be aligned with a study require neuro check for efficiency. The 36 hour CT and the 72 hour (end of catheter in-dwelling) CT must be obtained using a department scanner at optimal metal artifact reduction settings as it will be used for primary endpoint analysis. The 72 hours (± 4 hr) or end of catheter in-dwelling CT can be obtained after catheter removal to minimize the risk of compromising sterility of the fluid loop. However, if it obtained prior to catheter removal, steps to maintain sterility during patient transport should be followed as described in 7.5.9 below.

The venous blood sample should be submitted for a Complete Blood Count (CBC) with Differentials and a Comprehensive Metabolic Panel (CMP) to allow for comparison to pre-therapy values.

7.5.9 Patient Transport during Neurapheresis

If it is necessary to transport the study subject during the Neurapheresis procedure, ensure that the Sponsor's representative is present and the system is stopped for transport. Care should be taken to protect the integrity of tubing connections during transport. If possible, transport the system connected to the Subject, keeping the fluid loop intact or, remove the tubing and filters from the mounting bracket and place the components on the bed. If a system disconnect is required, connect the two catheter ends to one another (male→female) keeping the catheter sterile, see Figure 7. If sterility is compromised when connecting, the ends of catheter should be cleansed with Betadine for three minutes per AANA guidelines or SOC at center for sterile line technique when reconnecting to the Neurapheresis System.

The patient may sit up, stand, or move from their hospital bed as permitted or recommended by SOC. Center personnel should work with the MNeuro CFS to position the system cart in such a way to minimize strain on the catheter and tubing and allow proper movement of the patient. The system should remain connected to the patient, and depending on the type of movement, the system may continue running.

7.5.10 Catheter Removal

As described in Section 7.5.8, above, it is a protocol requirement to obtain a CT scan of the head within 4 hours of catheter removal (± 4 hr from catheter removal) to document the post-therapy status. This post-Neurapheresis CT will be compared to the pre-Neurapheresis CT (Baseline CT) to analyze applicable study endpoints. This CT cannot be obtained bedside.

An image of the catheter position prior to removal is required showing proximal (lumbar cistern) and distal catheter (thoracic anatomy) locations. It is preferable that this is captured by fluoro to be consistent with the intra-procedural images captured during catheter placement, but X-ray capture of the image is acceptable if better accommodates work flow at the center.

It is recommended that the Investigator employ the following steps for catheter removal and be mindful of any analgesic requirements for catheter removal. It is likely that removal of the Neurapheresis catheter will have the same pain profile as the removal of lumbar drains so the Investigator may want to consider analgesic coverage per their professional discretion. The steps to removing the catheter are outlined below and are not exclusive of the SOC for spinal catheter removal at each study site. The IFU should also be referenced for more detailed information on catheter removal.

- Stop pump
- Turn flow assembly stopcocks such that the flat aspect of the stop-cock is toward the subject.
- Disengage catheter from the flow assembly stopcock
- Join male and female catheter ends together to form a sterile loop
- Obtain image of final catheter position
- Remove dressings and any sutures or fixation mechanisms used to retain catheter
- Gently pull catheter until it exits the subject
- Hold pressure on site until dressing and/or stitch is applied
- Have Subject lie flat or on their side for 30 minutes
- Watch for signs of headache or Dural CSF leak. If a headache occurs or a blood patch is required to seal a leak, complete an Adverse Event CRF.

Upon removal, follow the steps to return the investigational catheter to the Sponsor. Confer with the MNeuro CFS to ensure proper packaging and documentation for return, in addition to making the appropriate annotations in the study Device Accountability Log.

In the event of a Subject death during Neurapheresis, the Technical Representative will work with the center to obtain the catheter in a timely fashion.

7.6 Post-Neurapheresis Surveillance Schedule

7.6.1 2 Day (± 1 day) Follow-up Data

The first surveillance metric will occur at 2 days (± 1 day) according to Table 11. It is expected that the Subject will still be in the Neuro ICU at this point. Along with the clinical status and hospital data on the CRF, requirements for this visit include a CT, venous blood sample, GCS and de-identified laboratory and other applicable SOC source documents. Data should be collected from SOC source documents and transferred to the CRFs however, if source documents are not available, completed study worksheets can be signed by the investigator and maintained in the study file as source documents for monitoring.

A protocol required CT is requested at this follow-up to document the status of any subarachnoid blood remaining following Neurapheresis. Care should be taken to obtain the CT at the same

angle as those previously completed to improve the comparability of the data. The CT can be obtained bedside for appropriately equipped investigational sites.

Additionally, a protocol required venous blood sample is to be taken at the 2 day follow-up and sent for analysis. (CBC with Differentials/CMP) with associated laboratory reports provided to the sponsor. As CSF cultures should be followed for 96 hours from the last sample, it is expected that additional CSF analysis laboratory reports would be included with the 2 day follow-up data. Any SOC imaging studies (CTs, TCD, etc.) and associated reports completed since catheter removal should be submitted. The medical record and clinical status should be reviewed for adverse events and reported on the appropriate case report form as applicable. Finally, non-adherence to the visit requirements will result in a protocol deviation.

7.6.2 Neuro ICU Discharge Follow-up Data

Subjects are expected to be discharged on average 10-14 days post aneurysm securement from the Neuro ICU (critical care unit). Discharge may be a change in location (i.e. to a stepdown unit, main hospital floor, rehabilitation facility or home) as dictated by clinical status and institutional SOC. Alternatively, Neuro ICU discharge may be based only on clinical status (i.e. the point at which the subject no longer meets the institutional definition for critical care monitoring). If the date of discharge from clinical status is different than the date of change to physical location, sites are expected to use the earlier of the two dates for the discharge date. Sites are asked to discuss institutional discharge criteria with a sponsor representative to ensure discharge data is collected at the appropriate time.

Data should be collected at the time of discharge and include the following assessments that may not be SOC are required. See Table 11 for detailed requirements; GCS and Modified Rankin Scale (mRS).

As CSF cultures should be followed for 96 hours from the last sample, it is expected that laboratory reports after the 2 day follow-up will be submitted with this discharge follow-up data. Additionally, any SOC imaging studies (CTs, TCD, etc.) and associated reports completed since the last study visit should be submitted. The medical record and clinical status since the last study visit should be reviewed for adverse events and reported on the appropriate case report form as applicable. Finally, non-adherence to the visit requirements will result in a protocol deviation.

7.6.3 30 Day (± 3 day) Follow-up Data

The final surveillance metric will occur at 30 days (± 3 days) post removal of the Neurapheresis System catheter according to Table 11. It is highly likely that the Subject will not be hospitalized at this follow-up and as such a return to the clinic is recommended to properly perform the required neurological assessments. (GOSE, mRS, Barthel, MoCA). If the subject refuses to or is unable to return, this follow-up may also be completed as able by phone however that should be a last option.

The medical record and clinical status should be reviewed for adverse events and reported on the appropriate case report form as applicable. Finally, non-adherence to the visit requirements will result in a protocol deviation.

Table 4: Data Collection Schedule

Data Items	Screening / Enrollment	Catheter Placement	Neurapheresis Procedure	2-Day Post-Neurapheresis (± 1 -day)	Discharge from Neuro ICU	30 Days Post-Neurapheresis (± 3 days)
Demographics, Medical Hx, SAH Symptomology	✓					
Aneurysm data; location, measurements, securement, etc.	✓					
Modified Fisher Grade	✓					
WFNS	✓					
Hunt & Hess	✓					
Glasgow Coma Scale (GCS)	✓		✓ [‡]	✓	✓	
Peripheral Check			✓ [‡]			
Glasgow Outcome Scale Extended (GOSE)						✓
Modified Rankin Scale (mRS)					✓	✓
Barthel Index						✓
Montreal Cognitive Assessment (MoCA)						✓
Activated Clotting Time Data (if applicable)		✓				
Catheter/System data		✓	✓			
CSF Sampling and Laboratory Reports		✓	✓	✓ ^β	✓ ^β	
CBC with Differential/CMP Blood Test and Laboratory Reports	✓		✓**	✓		
Protocol Required CTs Scans		✓*	✓***	✓		
SOC CT Scans	✓		✓	✓	✓	
Fluoroscopy or X-ray Image of Catheter		✓	✓ [©]			
ICP Data (if applicable)			✓ [‡]	✓	✓	
Clinical and Hospital Data e.g., LOS, location, vital signs, complications	✓		✓	✓	✓	✓
Protocol Deviations	✓	✓	✓	✓	✓	✓
Adverse Events		✓	✓	✓	✓	✓

* CT is required after aneurysm securement but prior to Neurapheresis initiation and must be assessed to ensure intracranial stability prior to beginning therapy

** Blood sample is required at 36 hrs (± 4 hr) and at the end of catheter indwelling or 72 hours (± 4 hr) whichever is earlier

*** CT is required at 36 hrs (± 4 hr) and at the end of catheter indwelling or 72 hours (± 4 hr) whichever is earlier [cannot be bedside CT]

† ICP (for subjects with EVD), Lumbar Pressure GCS and peripheral checks are required every 1 hours (± 1 hr) during catheter in-dwelling

‡ Reports for CSF cultures should be followed through 96 hours from the last sample taken prior to catheter removal

© Catheter image to document final catheter placement post-Neurapheresis therapy

8. ADVERSE EVENTS (AEs)

The Study will not track all-cause AEs or AEs related to SOC or the SAH clinical pathway e.g., re-bleed, deep vein thrombosis, skin breakdown etc. Study required event reporting is limited to AEs directly related to the investigational catheter, investigational system or Neurapheresis procedure, or study required element (such as CSF sampling). In cases where the event may have an attributable dual causality i.e., SAH clinical path or the Neurapheresis procedure, the center should report the event.

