The PILLAR study protocol, under which subjects were enrolled, limited catheter in-dwelling time to 36 hours and total pump time (therapy time) to 24 hours. As can be seen in the table above, the average pump time was shorter than anticipated with only one subject receiving the complete 24 hour allotted time for study therapy. Despite this, clearance of red blood cells (RBCs) from the lumbar cistern was seen as noted in the table below. Longer pump times will be necessary for more complete blood clearance. Pre and Post-Neurapheresis total protein measures were also taken to account for removal of by-products from lysed blood.

PILLAR Post-Neurapheresis Outcomes

Outcome Measured N=13	Pre-Neurapheresis mean \pm STD	Post-Neurapheresis mean \pm STD	Percent Decrease of Means
Concentration of Total Protein	537.36 \pm 500.70 mg/dL	144.09 \pm 188.44 mg/dL	73.2%
Concentration of CSF Red Blood Cells (RBCs)	2.78e5 \pm 2.43e5 cells/ μ L	1.17e5 \pm 1.30e5 cells/ μ L	57.9%

Subjects were followed at 2-weeks and 30-days post-Neurapheresis. Other notable outcomes include; a mean of 12 days to discharge from the Neuro ICU with a range of [6 – 18 days]. By the 2-week visit, 38.5% (5/13) were discharged home which increased to 69.2% (9/13) by 30 days.

PILLAR Follow-up Outcomes

Follow-up Status N=13	Two Week Median [range]	30 Day Median [range]
GCS	15 [11-15]	NR*
WFNS	1 [1-5]	NR*
mRS	2 [1-5]	1 [0-4]
GOS	NR*	5 [3-5]
Barthel	NR*	100 [20-100]

*These neuro assessments were not required per protocol

Finally, the primary safety endpoint for the study was the assessment of adverse events associated with the placement of the catheter and operation of the system. As there were no (0) adverse events associated with the placement of the catheter and minimal, expected, non-serious adverse

events (as seen below) during Neurapheresis, the end points of this study were considered to have been met.

The adverse events (AEs) reported below is site reported and was also reviewed by the independent DSMB. While the AEs were reported as potentially related to Neurapheresis therapy, they are also known AEs for subarachnoid hemorrhage patients.

PILLAR Device or Procedure Related Adverse Events During Neurapheresis

Event	Timeframe	Serious Adverse Event (SAE)	Related to System	Related to Neurapheresis	n/N (%)
Headache with Vomiting	Neurapheresis	No	No	Yes	1/13 (7.7%)
Vomiting	Neurapheresis	No	No	Yes	1/13 (7.7%)

PILLAR Device or Procedure Related Adverse Events After Neurapheresis

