4.3 Study Endpoints

The PILLAR-XT Study does not have a hypothesis based statistical endpoint due to the feasibility nature of the investigation.

Primary Endpoints:

1. Mean reduction of cisternal blood via CT post study therapy
2. Proportion of subjects with Neurapheresis Catheter, System or Therapy related serious adverse events

Secondary Safety Endpoints:

- Proportion of subjects with successful catheter placement of those attempted
- Proportion of subjects with study device or therapy related adverse events
- Proportion of subjects with systemic CNS infection within 5 day of catheter removal

Secondary Efficacy endpoints:

- Mean reduction of RBCs and total protein by CSF sample post study therapy
- Mean length of Neuro ICU stay

Exploratory endpoints:

- Proportion of subjects requiring additional CSF management during study therapy or on-going CSF management post study therapy
- Reduction in biomarkers of inflammation as seen in CSF, blood and physiologic manifestations post study therapy
- Proportion of subjects with symptomatic complications from aSAH
- Analysis of endpoints by the following sub-groups for any groups that have at least 5 subjects that meet the criteria for the group;
 - Age: <45, ≥ 45 -<60, 60 – 70 years

- Gender: male, female
- Enrollment Modified Fischer grade: 2, 3, 4
- Baseline cisternal Hijdra score: ≤15, 16-20, 21-25, 26-30
- Neurapheresis time: <16hrs, ≥16-28hrs, >28-40hrs, >40hrs
- Other sub-groups not yet defined

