 - CNS infection events will be reviewed by an independent medical monitor for whether or not the event meets the criteria above and will be used to calculate this endpoint (Number of subjects meeting CNS infection definition/Number of subjects in the Safety Population)

Secondary Efficacy endpoints:

- Mean reduction of RBCs and total protein by CSF sample post study therapy
 - This calculation utilizes the pre-Neurapheresis sample (first CSF sample taken either at the time of needle insertion or after catheter placement, whichever laboratory value is greater) as compared to the post-Neurapheresis sample (last CSF sample taken prior to catheter removal)

- Mean length of Neuro ICU stay
 - Mean length of Neuro ICU stay will be calculated by two different methods, one using physical location change, the second using criteria for critical care monitoring.

Exploratory endpoints:

- Proportion of subjects requiring additional CSF management during study therapy or on-going CSF management post study therapy
- Reduction in biomarkers of inflammation as seen in CSF, blood and physiologic manifestations post study therapy
 - Such as cytokines, white blood cell counts, neutrophil/lymphocyte ratio, SIRS
- Proportion of subjects with symptomatic complications from aSAH
 - Such as hydrocephalus, clinical vasospasm and delayed cerebral ischemia
- Analysis of endpoints by the following sub-groups for any groups that have at least 5 subjects that meet the criteria for the group;
 - Age: <45, ≥45-<60, 60 – 70 years
 - Gender: male, female
 - Enrollment Modified Fischer grade: 2, 3, 4
 - Baseline cisternal Hijdra score: ≤15, 16-20, 21-25, 26-30
 - Neurapheresis time: <16hrs, ≥16-32hrs, >32-48hrs, >48hrs
 - Other sub-groups not yet defined

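### Section 10.2 plans mean Neuro ICU stay under two discharge definitions, but section 7.6.2 sets one discharge date, the earlier of the two; if that date is the source, at least one mean is understated where the dates differ

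*Combined protocol and SAP*

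**What the plan says.** Section 4.3 lists "Mean length of Neuro ICU stay" as a secondary efficacy endpoint. Section 10.2 says that it will be "calculated by two different methods, one using physical location change, the second using criteria for critical care monitoring".

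Section 7.6.2 describes the same two ideas of discharge. The first is by place: "Discharge may be a change in location", for example to a stepdown unit or home. The second is by clinical status: "the point at which the subject no longer meets the institutional definition for critical care monitoring". Where the two fall on different days, "sites are expected to use the earlier of the two dates for the discharge date". The section then asks sites to discuss their discharge criteria with the sponsor so that discharge data are collected when they should be, and it requires GCS and mRS at discharge.

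Table 4 has one row that might hold further information, "Clinical and Hospital Data e.g., LOS, location, vital signs, complications". It is ticked at several visits, including Neuro ICU discharge and 30 days. The documents describe no separate field for a transfer date or a criteria date, and no indicator of which definition produced the discharge date.

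**The concern.** The two methods in section 10.2 can give different answers only for subjects whose two dates differ. Those are the subjects for whom section 7.6.2 replaces two dates by one. If the analyst takes the discharge date as section 7.6.2 defines it, both methods return the same mean and the planned comparison of definitions disappears. That common value is too short for at least one of the methods, because a minimum can only shorten a stay. The recorded date does not show which definition it meets, so the error could not be traced subject by subject from that field.

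At stake is the accuracy of one prespecified secondary efficacy result. No test, target or comparator depends on it.

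**Working it through.** The plan attaches no sample size, power or target to this endpoint, so there is no stated figure to reproduce. The check is logical, with an illustration of size.

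**Notation.** For each subject let L be the length of stay to the location change and C the length of stay to the day on which critical-care criteria are no longer met, both counted from the same starting point. The recorded value under section 7.6.2 is R = min(L, C).

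**Error in each mean if R is used for both methods**

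- Location method: mean(R) − mean(L) = −(share of subjects with C < L) × (mean gap in those subjects).
- Criteria method: mean(R) − mean(C) = −(share of subjects with L < C) × (mean gap in those subjects).

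For any one subject with differing dates, R is exactly right for one method and too early for the other. Across subjects:

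- If C never falls after L, the criteria-based mean is exact and only the location-based mean is short.
- If the order varies between subjects, both means are short.

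**Small example with mixed order (invented values, days)**

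| Subject | L | C | R |
|---|---|---|---|
| 1 | 12 | 12 | 12 |
| 2 | 12 | 10 | 10 |
| 3 | 12 | 11 | 11 |
| 4 | 10 | 12 | 10 |
| Mean | 11.50 | 11.25 | 10.75 |

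The location mean is short by 11.50 − 10.75 = 0.75 days. By the formula, the share is 2/4 and the mean gap (2 + 1)/2 = 1.5, which gives 0.75. The criteria mean is short by 11.25 − 10.75 = 0.50 days. By the formula, 1/4 × 2 = 0.50.

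**Range of size.** The share of subjects with differing dates and the gap between the dates are not in the documents. I assume shares of 10–50% and gaps of 1–3 days. The scale is the 12-day mean time to Neuro ICU discharge reported for PILLAR in section 2.1 (range 6–18 days).

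| Assumption on order | Location mean short by | Criteria mean short by |
|---|---|---|
| Criteria date always first | 0.10 × 1 = 0.1 to 0.50 × 3 = 1.5 days | 0 |
| Either date first, half and half | 0.10 × 0.5 × 1 = 0.05 to 0.50 × 0.5 × 3 = 0.75 days | 0.05 to 0.75 days |

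As a share of 12 days, the first row is 0.1/12 = 0.8% to 1.5/12 = 12.5%. A middle case, with 30% of subjects differing by 2 days and the criteria date first, gives 0.30 × 2 = 0.6 days, or 5%.

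**The case against.** The strongest reply is that section 7.6.2 is a visit-timing rule. It sits in the surveillance schedule, and its next sentence speaks of collecting discharge data at the right time. Section 10.2 is the place for endpoint derivation, and it keeps the two methods apart. A site must also know both dates to pick the earlier, and nothing forbids recording the other. Table 4 collects length of stay and location, from which a transfer date might be recovered. The case report form is not in the documents, so a second date field may exist.

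Much of this stands as possibility, and it limits confidence. It does not remove the conflict. The rule as written defines the discharge date without confining it to timing. Table 4 does not say whether length of stay means ICU or hospital stay, and it names no criteria date. A bed move after a status-based discharge falls between the discharge visit and the 30-day visit, where the synopsis asks for hospital data only if applicable.

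A reader might infer two stronger things. One is that neither mean can be computed correctly. The documents do not support that: the earlier date is always right for one method in each subject, and section 7.6.2 has location change follow from clinical status and local practice, so the criteria date may well come first as a rule and the criteria-based mean may be exact. The other is that sites may keep only the earlier date. The text says which date counts as the discharge date. It does not say that the other goes unrecorded.

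It is also fair to say that little depends on the result. Sections 4.3 and 10 state that the study has no hypothesis-based endpoint.

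**Conclusion.** The concern holds in a limited form. Sections 7.6.2 and 10.2 do not fit together: two lengths of stay are planned, one discharge date is defined, and no instruction covers the second date or a flag. If the discharge-date field is the source, at least one planned mean is understated wherever the dates differ. It is the location-based mean alone if the criteria date always comes first, and both if the order varies.

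The size depends wholly on assumed shares and gaps. With the criteria date first, the shortfall in the location-based mean is 0.1–1.5 days. The percentages use PILLAR's 12-day mean as a scale only, since section 2.1 does not say which discharge definition lay behind it.

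Severity is minor, because this is a descriptive secondary endpoint in a single-arm feasibility study. Confidence is moderate, because the case report form could already hold both dates.

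**What to change.** - **Section 7.6.2 and the discharge case report form:** record two dates in separate fields, namely physical transfer out of the Neuro ICU and the first day on which the institution's critical-care criteria are no longer met. State that the earlier date serves only to time the discharge assessments (GCS, mRS).
- **Section 10.2:** state that each mean uses its own date, and report the number of subjects with each date available.
- **Subjects already treated:** section 2.2 reports 16 treated under a previous version of the protocol. Retrieve both dates where they are charted and report how many are missing. The remaining 30 − 16 = 14 can be captured prospectively.

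If the form already has both fields, only the wording in the two sections needs to change.

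The cost is one extra date field and a sentence in each section. The likely weakness is incomplete criteria dates for the subjects already treated: a bed transfer is probably charted, but nothing in the documents shows that the day on which criteria ceased to be met is.

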6.1 Risks Associated with the Device, Components or Procedure

The table below outlines the risks that are associated with the Neurapheresis System (catheter, components and study procedure). In the event of a catheter or disposable replacement, the risk profile remains unchanged.

Table 2:Neurapheresis System Risks

Risks
Additional radiation exposure
Brainstem herniation
Headache
Nausea / Vomiting
Fluctuation in CSF volume or pressure
CSF leak
Retained catheter
Localized transient pain (back/leg)
Peripheral neuropathy / Paralysis
Re-Bleed / Hemorrhage
Infection / Sepsis
Subdural spinal hematoma
Death

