7.5.2 Neurapheresis Termination Criteria

Investigators should engage in an ongoing dialogue with the MNeuro CFS to address starting and stopping the pump for CSF sampling, change in clinical status, emergent situations and SOC concerns e.g., transport, extubation, physical therapy, study-required neuro checks or other. If a subject meets any of the criteria below, Neurapheresis should be stopped immediately (if not previously stopped) and the subject should be scheduled for catheter removal.

Change(s) in Subject conditions that require Neurapheresis termination are:

- Brainstem herniation
- Lower extremity paralysis
- Subdural spinal hematoma

- Subdural hematoma or hygroma
- Abnormal gram stain
- Re-bleeding event requiring intervention e.g., re-coiling, re-clip
- Subject previously non-intubated/extubated requires new or re-intubation
- ICP is greater than Lumbar pressure at five consecutive study-required neuro checks
- Subject requires inversion (such as Trendelenburg position)

As the MNeuro CFS will be on site during Neurapheresis therapy, the sponsor will be notified immediately if any subject has the Neurapheresis procedure terminated due to reasons above. Source documents may be requested for the Sponsor to adequately review the termination.

The Investigator may pause the system or terminate the procedure at any time. The Subject also has the right to terminate the procedure at any time. If study therapy must be terminated early, a head CT within (\pm 4hr) of catheter removal must be obtained to document the final amount and location of blood within the basal cisterns to allow for comparison to baseline.

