8.1 Adverse Event Definitions

Adverse Event (AE): Any untoward medical occurrence, unintended disease or injury, or untoward clinical signs in subjects, users or other persons, deemed related to the investigational device (catheter and/or placement accessories), Neurapheresis procedure, or study required element (such as CSF sampling).

Serious Adverse Event (SAE): Adverse event as defined above that

- a) led to death,
- b) led to serious deterioration in the health of the subject, that either resulted in:
 - 1) a life-threatening illness or injury, or,
 - 2) a permanent impairment of a body structure or a body function, or
 - 3) in-patient or prolonged hospitalization, or
 - 4) medical or surgical intervention to prevent life-threatening illness or injury or permanent impairment to a body function,
- c) led to fetal distress, fetal death or a congenital abnormality or birth defect.

Unanticipated Adverse Device Effect (UADE): Any serious adverse effect on health or safety or any life-threatening problem or death caused by, or associated with, a device, if that effect, problem, or death was not previously identified in nature, severity, or degree of incidence in the investigational plan or application (including a supplementary plan or application), or any other unanticipated serious problem associated with a device that relates to the rights, safety, or welfare of subjects" (21 CFR§ 812.3(s)).

Unanticipated Adverse Device Effects (UADE) that occur in subjects enrolled in the clinical trial should be reported under the IDE program (812.150) to FDA and all reviewing institutional review boards (IRBs) and investigators within 10 working days after you first receive notice of the adverse effect(s).

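### Primary endpoint 2 may understate the related-SAE rate, because the site's own relatedness judgement decides which events reach the independent monitor; the gap is clearest for non-fatal re-bleed and cranial subdural events

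*Combined protocol and SAP*

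**What the plan says.** Section 10.2 defines primary endpoint 2 as subjects with related SAEs divided by the Safety Population, with relatedness reviewed by an independent medical monitor. Section 13.2 gives that monitor the adverse events reported in the study.

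Three passages decide what is reported:

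- Section 8.1 defines an adverse event as an occurrence "deemed related to the investigational device (catheter and/or placement accessories), Neurapheresis procedure, or study required element (such as CSF sampling". The SAE definition builds on it.
- Section 8 restricts required reporting to directly related events and states: "The Study will not track all-cause AEs or AEs related to SOC or the SAH clinical pathway e.g., re-bleed". It adds that where "the event may have an attributable dual causality", the center should report.
- Section 8.2 and Table 5 list the required reports. Anything else is reported if the investigator considers it related.

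Elsewhere, Table 2 in Section 6.1 lists "Re-Bleed / Hemorrhage" and subdural spinal hematoma among the system's risks. The termination criteria in Section 7.5.2 include "Re-bleeding event requiring intervention e.g., re-coiling, re-clip", "Subdural hematoma or hygroma" and subdural spinal hematoma. On termination, "the sponsor will be notified immediately if any subject has the Neurapheresis procedure terminated due to reasons above".

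**The concern.** The plan gives relatedness to someone independent of the site, which is sensible in a single-arm study where every site knows that the subject was treated. The reporting rules then ask the site to settle relatedness first. The monitor can remove a reported event but cannot add one that never arrives, so any error from this filter runs in one direction, towards a lower rate.

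Causation is hard to separate in this population. Section 2.2 describes a herniation that was traced, after investigation, to evolving mass effect together with the device's pressure gradient. That event was reported and adjudicated, so it is not an example of a missed case. It does show that the device's contribution may not be plain to the site at the time. What is at stake is the credibility of the reported safety rate and its upper confidence limit, in a study whose objective includes further demonstrating safety.

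**Working it through.** **1. The route to the numerator.** An occurrence becomes an adverse event if held to be related (8.1). It is then reported (8, 8.2), adjudicated by the monitor (13.2) and counted if serious and related (10.2). The site controls the first two steps. Section 13.4 asks the investigator to assess the device relationship of every adverse event, which is circular if relatedness is already part of the definition.

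**2. The lists side by side.**

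| Event | Table 2 risk | 7.5.2 termination | Table 5 report |
|---|---|---|---|
| Non-fatal re-bleed | Yes | Yes, if intervention is required | No; Section 8 gives it as an example of what is not tracked |
| Cranial subdural hematoma or hygroma | Not by name | Yes | No |
| Spinal subdural hematoma | Yes | Yes | Not by name; paralysis, peripheral neuropathy, localized pain and insertion-site hematoma are listed |
| Brainstem herniation with re-bleed | Yes, as herniation | Yes, as herniation | No; the herniation entry is limited to cases without re-bleed |

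Death is in Table 5, so the gap concerns non-fatal events.

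**3. Other routes to the monitor.** Termination notice goes to the sponsor and covers only events that end therapy, while follow-up runs to day 30. Table 4 collects "Clinical and Hospital Data e.g., LOS, location, vital signs, complications" and standard-of-care CT scans, and Sections 7.6.1 to 7.6.3 require record review for adverse events at each visit. That review uses the same definition of an adverse event. No passage sends any of this material to the monitor. The monitor and DSMB charters are not in the documents.

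**4. Scale.** The plan gives no target, threshold or interval for this endpoint, so there is no design figure to reproduce. The one printed rate for an SAE checks: 1/16 = 6.25%, shown as 6.3% in Section 2.2. It covers events during therapy only and is not used below.

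Denominator: 30 Treated subjects (5.7.1) up to an expected 40 enrolled. The figure of 40 is an upper end, because it includes Intent to Treat subjects, who are outside the Safety Population. One further counted subject adds 1/30 = 3.3 points or 1/40 = 2.5 points.

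Exact (Clopper-Pearson) 95% limits for x of n are the 0.025 quantile of Beta(x, n−x+1) and the 0.975 quantile of Beta(x+1, n−x):

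| Subjects counted | n = 30 | n = 40 |
|---|---|---|
| 1 | 3.3% (0.1 to 17.2) | 2.5% (0.1 to 13.2) |
| 2 | 6.7% (0.8 to 22.1) | 5.0% (0.6 to 16.9) |
| 3 | 10.0% (2.1 to 26.5) | 7.5% (1.6 to 20.4) |

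If one subject were counted and one or two missed (assumed counts), a true second or third row would be reported as the first.

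**5. Range under assumptions.** Let q be the risk per subject of a related SAE of this kind, and s the chance that the site reports it. Neither is in the documents. The bias in the rate of such events is −q(1−s), and the chance of at least one unreported case is 1 − [1 − q(1−s)]^n. At n = 30:

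- q = 3%, s = 0.8: −0.6 points; chance 1 − 0.994^30 = 17%.
- q = 5%, s = 0.5: −2.5 points; chance 1 − 0.975^30 = 53%.
- q = 10%, s = 0.2: −8.0 points; chance 1 − 0.92^30 = 92%.

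The spread confirms that the size is unknown.

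**The case against.** The strongest reply is that little slips through. The dual-causality sentence sets a low bar: a re-bleed or subdural event during active CSF removal could easily have a device contribution, and the center should then report it. Table 6 in Section 13.4.2 has the AE form record relationship to the device, which suggests that the form takes the assessment rather than presupposing it. Terminations reach the sponsor at once, and imaging and records are submitted. Restricting capture to device-related events is a deliberate choice in a feasibility study with no hypothesis.

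Much of this stands, and it limits the point in two places. Section 7.5.5 calls spinal subdural hematoma a potential adverse event and has hourly checks to find it, and Table 5 catches most of its consequences, so that gap is small. A reader might also infer that herniation with re-bleed escapes independent oversight. It does not: the DSMB hold rule in Section 13.3 covers brainstem herniation without the re-bleed limit, although that rule does not feed the endpoint.

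What does not stand is that these safeguards close the gap. The site applies the dual-causality sentence, in the same paragraph that tells it re-bleed is not tracked, and no other safeguard is routed to the monitor.

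**Conclusion.** The point holds as a risk of underestimation, of unknown size and known direction. It is clearest for non-fatal re-bleed and cranial subdural hematoma or hygroma that the site attributes entirely to the hemorrhage. It merits correction because the remedy is cheap. Confidence is medium, since the charters might supply a route that the protocol does not.

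Four stronger readings are tempting and unsupported:

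- That re-bleeds are never reported. The dual-causality sentence can bring them in.
- That related events have already been missed among the 16 treated subjects. Nothing in the documents shows this.
- That the omissions from Table 5 are the whole cause. The main filter is the adverse event definition with Section 8's restriction. Read strictly, even Table 5 events must pass it, so new table entries alone might not suffice.
- That every missed event moves the rate by about 3 points. The endpoint counts subjects. The rate moves only if the event is serious, the monitor would call it related, and the subject is not already counted.

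The intervals above overlap widely and Section 10 sets no hypothesis, so the effect is on the reported rate and its upper limit, not on a decision.

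**What to change.** 1. Reconcile Section 8, Section 8.1 and Table 5 with Table 2 and Section 7.5.2. Require an AE form, whatever the site's attribution, for a named list: the present Table 5 events plus re-bleed or hemorrhage, subdural spinal hematoma, cranial subdural hematoma or hygroma, and brainstem herniation with or without re-bleed. Record relatedness on the form instead of requiring it in the definition. Remove re-bleed from the examples of what is not tracked.
2. Send every listed event and every Section 7.5.2 termination event to the existing medical monitor, and use the monitor's decision for endpoint 2.
3. For the 16 subjects treated under the previous protocol version, apply the same check to whatever complication, imaging and termination records are available. That version's data schedule is not shown. If the records are incomplete, report the rate by protocol version.

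The cost is a few more forms and adjudications for about 14 remaining subjects (30 − 16, matching the 5 + 9 in Section 7.5) and one look-back. Complications and standard-of-care CTs are already on the current schedule, so no new test is needed. The reported rate may be less favourable. No treatment or stopping rule changes.
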